with etelcalcetide improves bone hardness and mineralization using Ramen/nanoindentation and remodeling by histomorphometry using the quadruple label transiliac crest bone biopsy method in 20 ESKD patients with severe HPT.

Figure 2. Study timeline.

[figure not shown]

Table 1: Data Collection at each Study Visit

	Baseline	3 Months	9 Months
Informed consent	x		
Medical History	x		x
Physical Exam	x		x
Kt/V	x	x	x
Biomarkers of bone formation and resorption (BSAP, P1NP, CTX)	x	x	x

Procedures. This is a single-arm prospective cohort study to test the effects of 6-months of treatment with etelcalcetide on bone-tissue properties. We will obtain a single quadruple label bone biopsy to assess longitudinally the effects of 6-months of treatment with etelcalcetide on bone properties at the tissue level.

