We will enroll 20 adult patients with ESKD on hemodialysis who are scheduled to receive etelcalcetide for the treatment of HPT per standard of care. These 20 patients with ESKD will be treated with etelcalcetide to maintain levels of PTH between 300 and 400 pg/mL, which is at the mid-range of the KDIGO recommended range (2-9 times the ULN for the PTH assay¹) for 6 months. Patients will be identified for inclusion based on clinical need for the treatment of severe HPT and high turnover bone disease and only patients whose treating physician plans to initiate etelcalcetide will be included. HPT will be defined by the KDIGO guidelines (PTH >9-times the ULN for the PTH assay¹) and high turnover bone disease will be defined by a total alkaline phosphatase level \geq upper tertile of the reference range for the assay. At study start, patients will undergo the initial double labeling procedure with tetracycline (TCN; 3-days of TCN followed by 12-days off TCN followed by 3-days of TCN); during the labeling period etelcalcetide will not be administered (**Figure 2**). Patients will then undergo a 3-month etelcalcetide dose-titration phase to ensure that PTH levels are consistently maintained within target range (300-400 pg/mL), followed by a 6-month treatment (maintenance) phase. At the study endpoint (6-months of treatment), the final set of labels for transiliac crest bone biopsy will be given (3-days of demeclocycline followed by 12-days off demeclocycline followed by 3-days of demeclocycline) and bone biopsy will occur 5-days after the last dose of demeclocycline. During the final labeling period, the dose of etelcalcetide will continue to target the goal PTH level and the patient will continue to be managed as clinically indicated. The quadruple label approach permits longitudinal assessment of both dynamic indices of histomorphometry and bone-tissue level properties pre- and post-intervention, with the use of a single biopsy. The first label (TCN) is given prior to the initiation of etelcalcetide and the second label (demeclocycline) is given after 6-months of treatment (maintenance) with etelcalcetide. The fluorescence of tetracycline and demeclocycline differs, permitting differentiation of the labels under fluorescence microscopy and determination of dynamic indices of histomorphometry pre- and post-intervention. To assess bone tissue level effects of treatment, we will use a Raman/Nanoindentation system. This system allows the differentiation of tetracycline (pre-treatment) and demeclocycline (post-treatment) labels and permits precise measurement of localized bone tissue properties (e.g., mineral/matrix, collagen) and indentation properties (e.g., hardness) within these regions. Additionally, we will use 3-dimensional micro-CT (μ CT) imaging (resolution 3 μm^3) to obtain more complete structural indices from the bone biopsy specimens at the 6-month time point. Patients will have blood collected and stored at -80°C, at baseline (pre-treatment) and after 3- and 6-months of treatment (i.e., maintenance phase) (**Table 1**). Blood will be assayed for calcium, phosphorus, PTH, vitamin D metabolites, bone formation (bone specific alkaline phosphatase [BSAP], procollagen type-1 N-terminal propeptide [P1NP]) and resorption (C-Telopeptide [CTX]) markers, FGF-23 and sclerostin.

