Bone-tissue properties. We will use an integrated Raman/Nanoindentation system, which permits precise measurement of localized bone tissue properties (e.g., mineral/matrix, collagen) and indentation properties (e.g., hardness) within identical regions. Areas within the TCN and demeclocycline double label will be assessed for nanoindentation properties, and subsequently the same spatial location will be assessed for Raman-based measurements. Nanoindentation will occur using a Berkovich diamond indenter loading to a peak load of 10mN, a strain rate of 0.05 seconds and a holding period of 10 seconds. Oliver and Pharr methods will be used to determine the stiffness and hardness of the unloading curves. A total of 12-15 indentations will be performed within a given region. Following indentation, the same spatial regions will be assessed with Raman spectroscopy to determine the phosphate and matrix peaks after background and baseline shift correction. The ratio of phosphate:mineral will be calculated, along with other parameters (crystallinity and collagen crosslinking).

Hypothesis 2. Etelcalcetide will improve bone density, microarchitecture, and biomechanical competence in patients with ESKD.

Aim 2. To test if 6-months of treatment with etelcalcetide improves femoral neck areal BMD measured by DXA and failure load at the ultradistal radius measured by application of finite element analysis to HR-pQCT datasets. We will also quantify the effect of 6-months treatment with etelcalcetide on changes in areal BMD at the spine, total hip, and one-third and ultradistal radius measured by DXA, and cortical and trabecular volumetric BMD and microarchitecture, cortical porosity and tissue mineral density, and biomechanical competence at the ultradistal radius and tibia measured by HR-pQCT with application of finite element analysis.

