 1. Decreasing the dose of etelcalcetide can be implemented after the above steps have been undertaken. The dose should be lowered in 2.5 mg increments and monitoring of PTH and calcium should be obtained within a week of any changes.
 - d) Drop in serum calcium < 7.5 mg/dL or below the reference range with symptoms of hypocalcemia
 - i) Hold drug and monitor as per HD unit safety protocol
 - (1) If repeat calcium level WNL: restart dose at 2.5-5.0 mg lower than the previous dose and monitor as per HD unit safety protocol
 - (a) If repeat calcium level remains WNL and PTH at goal: no dose change
 - (b) If repeat calcium level remains WNL and PTH above goal: increase dose by 2.5 mg and monitor per HD unit safety protocol
 - (i) If calcium level < LLN but ≥ 7.5 mg/d without symptoms: follow algorithm 4c
 - (ii) If calcium level < 7.5 mg/dL or below the reference range with symptoms of hypocalcemia: proceed as per 4di
 - 5) Management of excessive suppression of PTH below the KDIGO target (< 2x LLN)

- i) Measure PTH after 4 weeks from initiation or dose adjustment
- ii) Without hypocalcemia: decrease dose by 2.5-5.0 mg and monitor as per HD unit safety protocol
- iii) With hypocalcemia: as per (4) above

Sample Size for Aim 1. N = 20

Sample Size Justification for Aim 1. The proposed sample size of 20 participants provides 80% power and 5% alpha for a two-tailed dependent T-test of the within-subject difference in the pre- and post-treatment hardness measured by Ramen/nanoindentation in the formation regions of 0.91-SDs. While we expect moderate variability in hardness between subjects, the within subject change due to treatment sought here is expected to be relatively similar across subjects given the established efficacy of etelcalcetide on other outcomes¹³. Behets et al¹⁴ reports patients with end stage renal disease show a baseline bone formation rate of 799 ± 334 (mean \pm SD), a O.Pm/B.Pm(%) of 18.9 ± 9.4 and a E.Pm/B.Pm of 13.1 ± 4.3 which assures a measurable region for the Ramen/nanoindentation assessment of hardness.

Sample Size for Aim 2. N = 35 (20 from Aim 1 plus 15 additional patients)

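### Aim 1's primary hardness test is described as a pre- to post-treatment change, but no hardness is measured before treatment, and tissue age coincides with the treatment label on the full schedule

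*Combined protocol and SAP*

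**What the plan says.** Aim 1, Procedures, sets up a single-arm study with one specimen per patient: "We will obtain a single quadruple label bone biopsy". The sequence is as follows.

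- First labelling, before drug: "3-days of TCN followed by 12-days off TCN followed by 3-days of TCN". In this period "during the labeling period etelcalcetide will not be administered".
- Titration: "Patients will then undergo a 3-month etelcalcetide dose-titration phase". Six months of maintenance follow.
- Final labelling with demeclocycline on the same 3-12-3 day pattern, with etelcalcetide continuing. Then "bone biopsy will occur 5-days after the last dose of demeclocycline".

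Of the Raman/nanoindentation system the same section says: "This system allows the differentiation of tetracycline (pre-treatment) and demeclocycline (post-treatment) labels and permits precise measurement of localized bone tissue properties". It presents the quadruple-label method as giving a longitudinal view of tissue-level properties as well as of the dynamic histomorphometry indices.

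The section on bone-tissue properties places the indentations inside the tetracycline and the demeclocycline double labels of that specimen, and adds: "Following indentation, the same spatial regions will be assessed with Raman spectroscopy".

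The list of endpoints names hardness as the sole primary endpoint of Aim 1. Statistical methods, For Aim 1, tests it with a two-tailed dependent t-test at 5%, as a change from a pre-treatment baseline to 6 months. The sample size justification describes the target as "the within-subject difference in the pre- and post-treatment hardness measured by Ramen/nanoindentation in the formation regions", with a detectable difference of 0.91 SD at n=20.

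**The concern.** A fluorescent label dates the deposition of bone. It does not date the measurement of its hardness, which is made when the specimen is indented. Both regions are indented after treatment, so the region tagged as pre-treatment is older bone that has been in the body through the whole treatment period. It is neither a baseline measurement nor an untreated comparator.

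The paired test therefore compares bone about ten months old, formed before the drug, with bone days to weeks old, formed under it. If hardness varies with tissue age at all, that variation enters the paired difference together with any drug effect. Pairing within the patient does not help, because the age difference lies inside the pair. At stake is what Aim 1's only primary endpoint can be said to show.

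**Working it through.** **The plan's own figure.** The justification gives 0.91 SD for 20 patients, 80% power, two-sided 5%, dependent t-test. For a paired test, power = P(|T| > 2.093), where T is noncentral t with 19 degrees of freedom and noncentrality d√20. This gives 80% at d = 0.66 and 97% at d = 0.91. The stated 0.91 is what an independent two-sample t-test with 20 per group would give (power 80.1%). That mismatch is a separate matter and errs on the safe side for power. It does not affect what follows.

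**Tissue age at biopsy** (inputs from Aim 1, Procedures; 1 month = 30.44 days).

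- Titration plus maintenance: 9 × 30.44 = 274 days.
- Each labelling period: 3 + 12 + 3 = 18 days. Last demeclocycline dose to biopsy: 5 days.
- Tetracycline bone, from the last dose: 274 + 18 + 5 = 297 days (9.8 months). From the first: 297 + 18 = 315 days (10.3 months).
- Demeclocycline bone: 5 days from the last dose, 5 + 18 = 23 days from the first.
- Gap between midpoints: 306 − 14 = 292 days (9.6 months).

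The two ranges do not overlap. If the biopsy fell exactly at the 9-month visit of Table 1, tetracycline bone would still be 9.0 to 9.6 months old.

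**Exception.** The Early Study Cessation Clause allows the biopsy after at least 3 months on drug, within 4 weeks after transplant. At that minimum, tetracycline bone is between about 91 days (3 months) and 91 + 28 + 18 = 137 days (4.5 months) old. The age gap would then differ between patients.

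**What an age effect would do.** The documents give no figure, so g below is an assumption: the shift in the paired difference due to age alone, in SDs of that difference. With no drug effect, the n=20 test rejects with noncentrality g√20:

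| g | g√20 | Probability of a significant result |
|---|---|---|
| 0 | 0 | 5% |
| 0.25 | 1.118 | 19% |
| 0.5 | 2.236 | 56% |
| 0.66 | 2.952 | 80% |
| 1.0 | 4.472 | 99% |

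With a true benefit of 0.91 SD and an age shift in the opposite direction:

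| Opposing shift | Net difference | Power |
|---|---|---|
| 0 | 0.91 | 97% |
| 0.25 | 0.66 | 80% |
| 0.5 | 0.41 | 41% |

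**Which measures are affected.** Hardness and the Raman measures are properties of the tissue as it stands at biopsy. Mineral apposition rate and bone formation rate rest on label spacing, which is set at deposition, so they are not confounded in the same way.

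**The case against.** The strongest reply is that no bias is shown. The documents do not say that hardness depends on tissue age. They establish that age and label coincide, not that age matters. The percentages above are simply the power curve of a paired t-test at n=20 and would describe any pre/post shift. All of this stands, and it is why the figures are given only as an assumed range. It does not rescue the description of the endpoint: whatever the size of an age effect, no hardness value is obtained before treatment. The plan neither assumes nor justifies a zero age effect.

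A second reply is that the single biopsy is deliberate, since it spares patients a second procedure (Protection against risk, Bone biopsy). That is a sound reason, and nothing here asks for another biopsy.

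A reader might infer that the test is likely to produce a false claim of benefit. The documents do not support that. If older bone is harder (assumed), false significant results would mostly point to a decline: with g = 0.25 and no drug effect, the chance of a false improvement is about 0.1%. The more relevant cost would then be lost power. But the sign cannot be settled from the documents.

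It is also tempting to repair the contrast by regressing the hardness difference on the Raman mineral/matrix difference and reading off the intercept. This should not be required. Equal mineralization need not mean equal age, and mineralization is itself an Aim 1 target, so the adjustment would remove part of the effect sought. The intercept may also be an extrapolation. Its standard error is √(1/20 + m²/19) residual SDs, where m is the mean mineral difference in its own SDs. That is 0.22 at m = 0, but 0.51 at m = 2 and 0.72 at m = 3 (values of m assumed).

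**Conclusion.** The point holds as a fault in how the primary contrast is defined and interpreted. It rests on the plan's own timetable: one biopsy, tetracycline bone of about 297 to 315 days, demeclocycline bone of 5 to 23 days, a single arm, and no text that deals with tissue age. On the full schedule, age and treatment label coincide in every patient, so the paired difference cannot by itself be read as an effect of etelcalcetide.

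The consequence for error rates and power is conditional on an age effect whose size and sign are unknown. A reader might go further and conclude that the Aim 1 hardness result will be biased by a known amount, or that the whole quadruple-label method fails. Neither follows: the first needs a figure the documents do not give, and the second overlooks the dynamic indices, for which the dating of deposition is what matters.

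**What to change.** For hardness and the Raman measures only, leaving the dynamic histomorphometry indices as they are, change the wording in three places:

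1. **Aim 1, Procedures:** the statement that tissue-level properties are assessed before and after the intervention, and the bracketed pre-treatment and post-treatment tags on the two labels.
2. **Statistical methods, For Aim 1:** the description of the hardness test as a change from pre-treatment baseline to 6 months.
3. **Sample Size Justification for Aim 1:** the reference to hardness before and after treatment.

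Suggested replacement: *bone formed before versus during treatment, both measured at the end-of-treatment biopsy, at tissue ages of about 10 months versus 5 to 23 days on the full schedule (a smaller gap for patients biopsied early under the transplant clause).*

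Add one sentence to the statistical methods: *the paired difference combines treatment and tissue age and will not by itself be attributed to etelcalcetide.*

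The cost is wording only, with no new biopsy, measurement or analysis. The downside is that the Aim 1 conclusion becomes more modest.

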Procedures. We will enroll 35 patients (20 from Aim 1 and 15 *de novo*) into this prospective single-arm cohort study to test the hypothesis that 6 months of treatment (maintenance) with etelcalcetide will decrease the propensity to calcify soft tissues as measured by T50. Similar to **Aim 1**, eligibility for enrollment into **Aim 3** will be based on a PTH level >9-times the ULN for the PTH assay (**Figure 1**), as well as their treating physician's plan to initiate etelcalcetide per standard of care. However, the presence of high turnover bone disease based on total alkaline phosphatase will not be a criterion for enrollment into **Aim 3**. Furthermore, all patients enrolled in **Aim 1** will be automatically enrolled into **Aim 3** unless they choose to opt-out of **Aim 3**. Thus, we will use the biochemical data from the 20 enrollees participating in **Aim 1** and enroll an additional 15 patients to be treated with etelcalcetide. As per **Aim 1** (**Figure 2**), after enrollment, patients will undergo a 3-month dose titration phase to ensure that PTH levels are stability maintained within the target range (300-400 pg/mL), followed by a 6-month treatment (maintenance) phase. Patients will have blood collected and stored at -80°C, at baseline (pre-treatment) and after 3- and 6-months of treatment (i.e., maintenance phase). Blood will be assayed for T50, calcium, phosphorus, PTH, vitamin D metabolites, bone formation (BSAP, P1NP) and resorption (CTX) markers, FGF-23 and sclerostin. We will assess the effect of treatment on changes in levels of T50, a clinically relevant biomarker of calcification propensity^{9, 10}. We will also determine relationships between changes in T50 and changes in phosphorus, calcium, bone turnover markers and calcitropic hormones.

Exploratory. None

Primary and Secondary Endpoints for Each Aim

Aim 1

1. Primary Endpoints: Hardness
2. Secondary Endpoints: Bone formation rate, mineralization density

Aim 2

1. Primary Endpoints: Changes in: (a) femoral neck areal BMD by DXA and (b) radius failure load by HR-pQCT
2. Secondary Endpoints: Changes in: (a) spine, total hip, and one-third and ultradistal radius BMD by DXA and (b) radius and tibia cortical density, thickness, porosity and tissue mineral density, and trabecular density, thickness, number and spacing

Aim 3

1. Primary Endpoint: Change in T50 (percent and absolute)
2. Secondary Endpoints: Changes in PTH, calcitropic hormones, FGF-23, Sclerostin, calcium and phosphorus

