For Aim 3. A two-tailed dependent T-test of the change in primary calcification propensity (T50) and secondary biochemical indices (calcitropic hormones, FGF-23, sclerostin, calcium and phosphorus) from pre-treatment baseline to the 6-month endpoint will be reported with an alpha-level of 5% as the criterion for statistical significance. Secondary exploratory analyses will assess the within-subject temporal course of change in the biochemical outcome with linear mixed models for repeated measures with time as a fixed effect (0, 3 and 6 months); the baseline value of the dependent variable entered as a continuous covariate; and a covariance structure determined by empirical testing performed prior to inferential testing. We will also assess whether the **Aim 1** participants differ from the patients recruited *de novo* for **Aim 3** with an independent T-test both of the two groups' baseline values and of the two groups' change in values from baseline to the 6-month endpoint. We will explore the covariances between changes in T50 and other biochemical markers of bone turnover and calcitropic hormones with simple and multiple regression with synchronized and lagged observations in time to determine whether leading, cotemporaneous or following patterns exist among these measures.

Subject Recruitment and Selection

Study site and number of patients eligible for enrollment. ESKD patients receiving hemodialysis at the Rogosin Institute, meeting enrollment criteria, and whose treating physicians intend to initiate treatment with etelcalcetide will be asked to participate in this study. Rogosin is the largest provider of hemodialysis in New York City and provides hemodialysis services to over 1300 patients. Approximately 25% of patients at Rogosin have PTH levels > 9-times the ULN for the PTH assay. Therefore, there are adequate numbers of patients at Rogosin who may be able and willing to participate in this prospective cohort study.

Enrollment Criteria

Inclusion criteria

For All Aims:

1. Patient has provided informed consent.
2. Patient is 18 years of age or older.
3. Patient must be receiving maintenance hemodialysis for at least 3 months, with adequate hemodialysis with a delivered Kt/V 1.2 or urea reduction ratio (URR) 65% within 4 weeks prior to screening laboratory assessments.
4. Dialysate calcium concentration must be stable for at least 4 weeks prior to screening laboratory assessments.

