Sample Size Justification for Aim 2. The proposed sample size of 35 participants provides >80% power and 5% alpha to detect a change in femoral neck BMD of 0.5% f and a 0.5 standard deviation change in radius failure load by HR-pQCT from pre-treatment to the 6-month endpoint. For femoral neck BMD by measured by DXA, Lien et al¹⁵ reported that in 8 patients with CKD treated with cinacalcet for 6 months, areal BMD at the femoral neck increased $2.2 \pm 1.1\%$ ($p < 0.05$). For failure load outcomes, in a longitudinal study of 29 patients with ESKD who underwent kidney transplantation, we reported that failure load decreased by $3.5 \pm 7.0\%$ ($p=0.0081$) over 12-months¹⁶; our larger sample size will permit detection of at least a 3.4% change in radius failure load due to suppression of PTH production by etelcalcetide.

Sample Size for Aim 3: N = 35 (20 from Aim 1 plus 15 additional patients)

Sample Size Justification for Aim 3: The proposed sample size of 35 participants provides >80% power and 5% alpha two-tailed dependent T-test of the change in T50 from baseline to the 6-month endpoint. Based on Smith et al¹⁰, each standard deviation (SD) decrease in T50 was associated with a 39% increase in odds of all-cause mortality. Assuming that the variability in T50 in patients on hemodialysis patients enrolled into this prospective cohort study are similar to those reported in Smith et al¹⁰, approximately 20 patients would be required to detect a 1-SD decrease in T50. Our sample size of 35 patients will permit the detection of a 0.7-SDs decline in T50. We assume that a reduction of lesser magnitude is of unclear clinical significance

Protection of Human Subjects

This study qualifies as clinical research and will be conducted in compliance with GCP and all regulatory requirements for the protection of human subjects.

Informed Consent

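### Aim 3 makes T50 change primary on both the percent and absolute scales with no deciding rule; if percent change is tested, the error rate can exceed 5% and usually leans toward benefit

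*Combined protocol and SAP*

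**What the plan says.** The list of primary and secondary endpoints gives the Aim 3 primary as "Change in T50 (percent and absolute"). Both scales carry primary status.

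The Aim 3 paragraph of the statistical methods plans "A two-tailed dependent T-test of the change in primary calcification propensity (T50") from baseline to the 6-month endpoint, which "will be reported with an alpha-level of 5% as the criterion for statistical significance". It names no scale.

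The opening paragraph of the statistical methods, which covers all aims, sets a step-down multiplicity adjustment within measurement domains. The domains listed are DXA, HR-pQCT and histomorphometry; T50 is not among them. The same paragraph allows data-guided normalising transformations but names none for T50.

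The Aim 3 sample size justification powers one test: "The proposed sample size of 35 participants provides >80% power and 5% alpha two-tailed dependent T-test of the change in T50". It also says "Our sample size of 35 patients will permit the detection of a 0.7-SDs decline in T50". The effect is in SD units, and again no scale is named.

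**The concern.** Absolute and percent change are different estimands with different null behaviour. Percent change divides by each patient's own baseline. A baseline that is low by chance inflates the ratio more than an equally high one deflates it. With similar variability before and after treatment, mean percent change is therefore positive even when T50 has not moved.

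Upward is the favourable direction, because the plan cites that "each standard deviation (SD) decrease in T50 was associated with a 39% increase in odds of all-cause mortality". The study is single-arm, so no control group carries the same bias and cancels it.

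At stake is whether a 5% claim on the Aim 3 primary really is a 5% claim, and what is concluded if one scale is significant and the other is not.

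**Working it through.** **Inputs.** From the documents: n = 35, two-sided 5%, paired t-test. The plan rests on an assumption ("Assuming that the variability in T50 in patients on hemodialysis patients enrolled into this prospective cohort study are similar to those reported") but prints no mean, SD or pre/post correlation for T50. CV and correlation below are therefore assumptions, shown over a range.

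**The plan's own figure.**
- Read 0.7 SD as the between-patient SD with zero pre/post correlation. The SD of the change is √2 × SD, the standardised effect is 0.7/√2 = 0.495, and the noncentrality is 0.495 × √35 = 2.93. Power is 81.2%.
- On that reading a 1-SD change needs 18 patients; the plan says "approximately 20 patients would be required to detect a 1-SD decrease in T50".
- Read as SDs of the change itself, the noncentrality is 0.7 × √35 = 4.14 and power is 98.0%.

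The statement of more than 80% power holds either way. It concerns one test and does not settle the scale.

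**Bias of percent change.** With equal means and no treatment effect,

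mean percent change ≈ CV₀² − ρ·CV₀·CV₁,

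where CV₀ and CV₁ are the baseline and follow-up CVs and ρ is the correlation. With equal CVs this is CV²(1 − ρ). At CV 0.20 and ρ = 0.5 it is 0.04 × 0.5 = 2.0%; simulation gives 2.0% (lognormal) to 2.3% (normal). The sign turns negative once ρ·CV₁ exceeds CV₀.

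**Simulated error rates.** n = 35, no true change, equal variability before and after; paired t-test on absolute change and one-sample t-test on percent change.

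| Assumed CV, correlation | Absolute, two-sided | Percent, two-sided | Percent, favourable tail (nominal 2.5%) | Either scale, two-sided |
|---|---|---|---|---|
| 10%, 0.5–0.8 | about 5% | 5.1–5.4% | 3.4–4.1% | 5.8–6.4% |
| 15–25%, 0.5–0.8 | about 5% | 5.5–8.6% | 3.9–7.9% | 6.5–10.4% |
| 20%, 0.5 | about 5% | 7.3–7.4% | 6.4–6.5% | 8.9–9.0% |
| 10–30%, 0.3–0.7 | 4.8–5.1% | 5.3–12.0% | 3.6–11.7% | 6.1–14.2% |

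A repeat with 60,000 trials per setting agreed with the first three rows to within about 0.2 percentage points.

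**Which part does the damage.** The two t statistics correlate at 0.93–0.996. With lognormal T50, CV 25% and ρ = 0.5, the favourable-tail rate is 8.0% for percent change alone and 8.0% for success on either scale. The false benefit comes from the percent test, not from having two tests. Splitting alpha therefore leaves the lean in place. In the repeat run at CV 20% and ρ = 0.5, testing each scale at two-sided 2.5% brings the either-scale total to 4.5–4.7%, but the percent test still puts 3.2–3.4% in the favourable tail against its 1.25% share.

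**The transformation step.** Taking logs only when an Anderson-Darling test rejects normality of percent change still leaves 3.6–8.4% in the favourable tail over CV 10–30% and correlation 0.3–0.7.

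**Unequal variability.** At baseline CV 20%, ρ = 0.8 and follow-up SD 1.3 times baseline, the formula gives 0.04 − 0.8 × 0.20 × 0.26 = −0.16%. Simulation gives −0.2%, with 2.3% of trials in the upper tail and 2.9% in the lower. At 1.5 times baseline the bias is −0.9% and the tails are 1.5% and 3.9%. At ρ = 0.5 and 1.3 times baseline, the upper tail is still 4.4%.

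**The case against.** A reader might infer that the Aim 3 type I error is above 5% and tilted toward benefit as the plan stands. The documents do not support that. They plan one paired t-test, which applied to raw before-and-after values tests absolute change and holds about 5%. Nowhere do they say that percent change will be tested or that either scale suffices. The endpoint line joins the scales with a conjunction; if both had to be significant, the error would be about 3–4%.

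The direction is not guaranteed either, as the unequal-variability cases show. The size rests on CVs and correlations the documents do not give, and at CV 10% it is minor. At CV 20% the plan's 0.7-SD target is 0.7 × 20% = 14% of the mean, against a null bias of about 1–2%.

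All of that stands and makes the claim conditional. It does not close the gap. Percent change is a stated primary endpoint, and nothing marks it as descriptive. Testing it is a realistic reading: the Aim 2 sample size justification cites percent changes with p-values (2.2 ± 1.1%, p<0.05; 3.5 ± 7.0%, p=0.0081).

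**Conclusion.** The plan leaves the Aim 3 primary test open between two scales that behave differently. The error rate is about 3–4% if both must succeed, about 5% if absolute change decides, and above 5% if percent change is tested as a primary or either scale suffices.

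In that last case, with CV 15–25%, correlation 0.5–0.8 and equal variability, the percent test rejects in about 5.5–8.6% of null trials (3.9–7.9% in the favourable tail), and either scale in about 6.5–10.4%. The excess is small at CV 10%. The lean needs roughly similar variability before and after. The main problem is bias in the percent-change test; having two tests is secondary.

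**What to change.** In the endpoint list, make absolute change in T50 the single Aim 3 primary, and say in the Aim 3 methods that the paired t-test applies to it. Change in log T50 is an acceptable alternative if prespecified; it also holds about 5% (4.6–5.2% in simulation). Report percent change descriptively only, as a ratio of means or a back-transformed mean log-ratio, with no test of its own.

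This takes a line or two of text. The sample size of 35 and the stated 0.7-SD detectable effect are unchanged. The one small cost is that absolute change may be slightly less efficient than a log-ratio if the effect is proportional.

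In the same edit, reconcile the wording of the Aim 3 sample size justification. It speaks of detecting a fall in T50, although its own mortality statement makes a fall the harmful direction.
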